8.2.1. Selection Criteria for Targeted HCPs

The target study population will be specialist HCPs in Europe who are prescribers of Xeljanz for the treatment of RA, PsA, or UC (e.g., rheumatologists, dermatologists, and gastroenterologists), as these will be the HCPs who were targeted for the aRMM materials distribution by the MAH. All HCPs from the proprietary IQVIA OneKey database who meet the eligibility criteria will be invited to participate in the survey (i.e., the **Targeted HCPs**). A description of the IQVIA OneKey database can be found in [Section 8.4](#) (Data Sources).

8.2.1.1. Inclusion Criteria

The following are the study inclusion criteria for the **Targeted HCPs**:

1. HCPs in the OneKey database who have “rheumatology,” “dermatology,” or “gastroenterology” listed as their primary, secondary, or tertiary specialty;
2. HCPs who have contact information available in the OneKey database (at least 1 of: email, mailing address, or phone number); and
3. HCPs who are located in the selected countries.

8.2.1.2. Exclusion Criteria

The following is the study exclusion criterion for the **Targeted HCPs**. HCPs are excluded if they meet the following criterion:

1. HCPs who participated in pilot testing of the Xeljanz PASS HCP survey (current study; Protocol Number: A3921334).

8.2.2. Inclusion and Exclusion Criteria for the Final Study Population

The **Final Study Population** will be used for all study analyses and will consist of those **Targeted HCPs** who submitted a completed survey. Inclusion/exclusion criteria for the **Final Study Population** are described below.

8.2.2.1. Inclusion Criteria

The following are the study inclusion criteria for the **Final Study Population**:

1. HCPs who are **Targeted HCPs**;⁴
2. HCPs who agree to participate in the survey voluntarily by answering “Yes” to Consent Question, “Do you agree to proceed with this survey?”;
3. HCPs who have written at least 1 prescription for Xeljanz for patients with RA and/or PsA or UC in the 12 months preceding the survey administration; and
4. HCPs who submitted a completed survey (i.e., answered *all* survey questions).

8.2.2.2. Exclusion Criterion

The following is the study exclusion criterion for the **Final Study Population**:

1. HCPs who are current employees of Xeljanz’s MAH (i.e., Pfizer).

8.3. Variables

The variables to be analysed will include:

1. HCP practice characteristics.

- Specialty (i.e., In the RA/PsA Survey: rheumatology, dermatology or other and in the UC survey: gastroenterology, or other);
- Number of years in practice;
- Experience prescribing Xeljanz within the past 12 months for RA and/or PsA or UC;
 - This variable will be used as a proxy for indication. An HCP who has experience prescribing Xeljanz for multiple indications (of RA and PsA) will be classified in the indication that corresponds to the HCP’s highest specialty designation in the OneKey database;
- Self-reported most recent prescription for Xeljanz for RA and/or PsA or UC;
- Self-reported approximate number of Xeljanz prescriptions written for RA and/or PsA or UC in the past 12 months;

⁴ HCPs who respond to the survey but are not rheumatologists, dermatologists, or gastroenterologists (e.g., nurse practitioners, physician’s assistants, physicians of other specialties) will be allowed to participate if they are prescribers of Xeljanz for patients diagnosed with RA and/or PsA or UC and meet the study inclusion/exclusion criteria.

- Self-reported approximate number of patients prescribed Xeljanz for RA and/or PsA or UC in the past 12 months;
- Role in providing Xeljanz treatment (i.e., only initiation, both initiation and maintenance, only maintenance); and
- Prior participation in a Pfizer-sponsored tofacitinib clinical trial as a healthcare professional.

Note: There are 2 questions that ascertain information on the HCP's specialty and years of practice and 7 questions in the RA/PsA survey and 6 questions in the UC survey that ascertain information on the HCP's experience prescribing Xeljanz (see survey instrument in Appendix 1 and Appendix 2 [HCP Questionnaire for RA/PsA and UC, respectively]).

2. aRMM program implementation.

- Awareness (receipt) of each of the aRMM materials *ever* (i.e., whether the respondents recalled receiving each of the following aRMM materials: the Xeljanz Prescriber Brochure, the Xeljanz prescriber treatment checklists, and the Xeljanz Patient Alert Card);
- Awareness (receipt) of each of the aRMM materials *after February 2020 (or after January 2020 for Poland)*;
- Utilisation of each of the aRMM materials (i.e., whether the respondents read the Xeljanz Prescriber Brochure, utilised the Xeljanz prescriber treatment checklists when prescribing Xeljanz), and distributed the Xeljanz Patient Alert Card to their patients); and
- Awareness and utilisation of the Xeljanz Prescriber Website (i.e., whether the respondents were aware of and visited the Xeljanz Prescriber Website).

Note: There are 14 questions for all countries, except for Germany, which only has one aRMM HCP checklist rather than two (see survey instrument in Appendix 1 and Appendix 2 [HCP Questionnaire for RA/PsA and UC, respectively]) that ascertain awareness [receipt] and utilisation of the aRMM materials and Xeljanz Prescriber Website, except for Germany, which has 12 questions. One of the utilisation questions is also counted as an adherence question (see Table 2).

3. Knowledge of the key risk messages pertaining to the use of Xeljanz (including the risk minimisation practices to prevent/minimise risks associated with Xeljanz).

- HCPs providing correct answers for each knowledge question, or each knowledge response option associated with a survey question (as applicable).

	RA/PsA survey	UC survey

 HCPs correctly answering ≥70% to <80% of the knowledge questions 	Correctly answering 13-14 out of 18 knowledge questions	Correctly answering 14-15 out of 20 knowledge questions

 HCPs correctly answering ≥80% to <90% of the knowledge questions 	Correctly answering >80 but <90% 15-16 out of 18 knowledge questions	Correctly answering 16-17 out of 20 knowledge questions

 HCPs correctly answering ≥90% to <100% of the knowledge questions 	Correctly answering 17 out of 18 knowledge questions	Correctly answering 18-19 out of 20 knowledge questions

 HCPs correctly answering 100% of the knowledge questions 	Correctly answering 18 out of 18 (100%) of the knowledge questions	Correctly answering 20 out of 20 (100%) of the knowledge questions

Note: For the RA/PsA survey, there are 18 questions that ascertain knowledge about the key risk messages (see Table 3). For the UC survey, there are 20 questions that ascertain knowledge about the key risk messages (see Table 4). Each key risk message and associated survey question(s) is described in more detail in Appendix 3 and Appendix 4 (Key Risk Messages for the RA/PsA survey and the UC survey, respectively).

4. Self-reported adherence to the risk minimisation practices recommended in the aRMM materials (e.g., provision of patient counselling and the alert card to patients, patient screening, laboratory monitoring recommendations, and limitations of use).

- HCPs providing desirable responses for each adherence question, or each adherence response option associated with a survey question (as applicable).

	RA/PsA survey	UC survey

 HCPs providing desirable responses to ≥70% to <80% of the adherence questions 	Providing desirable responses to 12-13 out of 17 adherence questions	Providing desirable responses to 12-13 out of 17 adherence questions

 HCPs providing desirable responses to ≥80% to <90% of the adherence questions 	Providing desirable responses to 14-15 out of 17 (adherence questions)	Providing desirable responses to 14-15 out of 17 adherence questions

 HCPs providing desirable responses to ≥90% to <100% of the adherence questions 	Providing desirable responses to 16 out of 17 adherence questions	Providing desirable responses to 16 out of 17 adherence questions

 HCPs providing desirable responses to 100% of the adherence questions 	Providing desirable responses to 17 out of 17 adherence questions	Providing desirable responses to 17 out of 17 adherence questions

Note: There are 17 questions that ascertain adherence to the risk minimisation practices recommended in the aRMM materials in both the RA/PsA and UC surveys. One of these

questions is also counted as a utilisation question (see Table 3 [RA/PsA survey] and Table 4 [UC survey]).

5. Effectiveness of the aRMM program in *each* of the following 4 domains:

	RA/PsA survey	UC survey

 Awareness (Receipt) ever 	
≥80% of HCPs reporting that they received 4 out of the 4 (100%) aRMM materials⁵ in all countries, except for Germany⁶
 
≥80% of HCPs reporting that they received 3 out of the 3 (100%) aRMM materials⁶ in Germany
	
≥80% of HCPs reporting that they received 4 out of the 4 (100%) aRMM materials⁵ in all countries, except for Germany⁶
 
≥80% of HCPs reporting that they received 3 out of the 3 (100%) aRMM materials in Germany⁶


 Awareness (Receipt) after February 2020 	
≥80% of HCPs reporting that they received 4 out of the 4 (100%) aRMM materials⁵ in all countries, except for Germany
 
≥80% of HCPs reporting that they received 3 out of the 3 (100%) aRMM materials⁶ in Germany
	
≥80% of HCPs reporting that they received 4 out of the 4 (100%) aRMM materials⁵ in all countries, except for Germany
 
≥80% of HCPs reporting that they received 3 out of the 3 (100%) aRMM materials⁶ in Germany

 Knowledge 	
≥80% of HCPs correctly answering ≥14 out of 18 (≥78% [or approximately 80%]) of the knowledge questions
	
≥80% of HCPs correctly answering ≥16 out of 20 (≥80%) of the knowledge questions

 Adherence 	
≥80% of HCPs providing desirable responses for ≥14 out of 17 (≥82% [or approximately 80%]) of the adherence questions
	
≥80% of HCPs providing desirable responses for ≥14 out of 17 (≥82% [or approximately 80%]) of the adherence questions

Note: The measures of effectiveness in each of the 4 domains listed above will be calculated variables.

⁵ The 4 aRMM materials include: the Xeljanz Prescriber Brochure, the Xeljanz Prescriber Treatment Initiation Checklist, the Xeljanz Prescriber Treatment Maintenance Checklist, and the Xeljanz Patient Alert Card. As the Xeljanz Prescriber Website is a repository for the aRMM materials, rather than a tool in and of itself, awareness of the Xeljanz Prescriber Website will not be considered when evaluating the effectiveness of the entire aRMM program.

⁶ The 3 aRMM materials include: the Xeljanz Prescriber Brochure, the Xeljanz Prescriber Treatment Initiation and Maintenance Checklist, and the Xeljanz Patient Alert Card. As the Xeljanz Prescriber Website is a repository for the aRMM materials, rather than a tool in and of itself, awareness of the Xeljanz Prescriber Website will not be considered when evaluating the effectiveness of the entire aRMM program.

6. Attitude toward the aRMM materials (i.e., how useful the HCPs find the various aRMM materials in their practice).

- There are 5 survey questions (1 question for each of the aRMM materials plus 1 question for the Xeljanz Prescriber Website) that ascertain HCPs' attitudes towards the aRMM materials, except for Germany, which has 4 questions.

7. Source of HCPs' information on the safety of Xeljanz.

- There is 1 survey question that asks HCPs to identify their primary source of safety and prescribing information regarding Xeljanz from a list of pre-populated choices.

Response rate, eligibility rate, completion rate. The HCPs' participation in the survey study will be examined by calculating the following mutually exclusive categories of HCPs

Survey administration statistics

- The number of invitations issued (I);
- The number of invitations returned as undeliverable (R)
- The number of respondents screened for participation (S);
 - **Survey response rate** = $S/(I-R)$;
- The number of respondents eligible for participation (E);
 - **Eligibility rate** = E/S ;
- The number of eligible respondents who completed the survey (C);
 - **Completion rate** = C/E ;

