8.7. Data Analysis

8.7.1. General Statistical Consideration

Detailed methodology for summary and statistical analyses of data collected in this study will be documented in a statistical analysis plan (SAP), which will be dated, filed, and maintained by the Sponsor. The SAP may modify the analyses outlined in this protocol; any major modifications of primary endpoint definitions or their analyses will be reflected in a protocol amendment.

The data collected from the RA/PsA survey will be analysed separately from the data collected from the UC survey. For each survey (RA/PsA and UC), all primary analyses will be conducted using the *pooled* data from all countries, specialties (applies to the RA/PsA survey only), and indications (applies to the RA/PsA survey only), and will be descriptive in nature; no statistical comparisons within or between countries, specialties, and/or indications will be conducted. Only submitted and completed surveys—i.e., all of Questions of the survey (Appendix 1 and Appendix 2 [HCP Questionnaire for the RA/PsA survey and the UC survey, respectively]) answered (taking into account skip patterns) by HCPs eligible to participate in the survey—will be used in the analyses.

Categorical variables will be presented using frequencies and proportions. For most outcomes, associated 95% CIs will also be calculated; 95% CIs will *not* be calculated for outcomes such as attitude towards the aRMM materials and Xeljanz Prescribe Website and source of HCPs’ information on the safety of Xeljanz. Continuous variables will be presented using means, standard deviations (SDs), minimums, 25th percentiles, medians,

75th percentiles, and maximums. Depending on the sample size, stratification by country, number of patients treated with Xeljanz, experience prescribing Xeljanz (a proxy for indication), receipt and utilisation of the aRMM materials, and/or number of years in practice may be performed. The analysis may also be restricted to HCPs without prior experience as a healthcare professional in a Xeljanz clinical trial, if sample size is sufficient.

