ANNEX 3. ADDITIONAL INFORMATION

Appendix 1. HCP Questionnaire for Rheumatoid Arthritis and/or Psoriatic Arthritis

[SCREENING QUESTION]

[QUESTION APPLIES TO ALL COUNTRIES]

Before starting the survey, we need to ensure that you are eligible for this survey by asking you the following question:

S1. Are you currently employed by Pfizer?

No *Continue*

Yes Thank you for your interest. Unfortunately, you are not eligible to participate.
Close (SCREEN OUT)

(yes/no tick box)

If you have any questions, please contact: IQVIA Team at: xxxxx *[to be adapted to the country]*.

Kind regards,

IQVIA Team

Start of Interview:

[QUESTIONS ABOUT HCP PRACTICE CHARACTERISTICS]

[QUESTION APPLIES TO ALL COUNTRIES]

Thank you for your interest in this study. This survey should take about 25 minutes to complete and consists of 5 sections. It should be completed in one sitting.

The first section includes questions about your professional background and practice.

D1. What is your main medical specialty? Please select one.

a	Rheumatologist	
b	Dermatologist	
c	Other	

Data: Single punch.

[QUESTION APPLIES TO ALL COUNTRIES]

D2. After completing all specialist training, for how many years have you been in practice? Please select one.

a	Less than 1 year	
b	1 year to less than 5 years	
c	5 years to 10 years	
d	More than 10 years	

Data: Single punch.

[QUESTIONS ABOUT EXPERIENCE WITH XELJANZ (TOFACITNIB)]

Thank you. The second section of questions asks about your experiences with Xeljanz (tofacitinib).

[QUESTION APPLIES TO ALL COUNTRIES]

S2. Within the past 12 months, have you prescribed tofacitinib for rheumatoid arthritis and/or psoriatic arthritis? Please consider both new and repeat prescriptions.

a	No		Thank you for your interest. Unfortunately, you are not eligible to participate. Close (SCREEN OUT)
b	Yes		Continue

(yes/no tick box)

[QUESTION APPLIES TO ALL COUNTRIES]

S3. Please indicate the diagnosis for which you prescribed tofacitinib in the past 12 months. Please consider both new and repeat prescriptions. Select all responses that apply.

a	Rheumatoid arthritis		Continue
b	Psoriatic arthritis		Continue

Data: Multiple punch.

[QUESTION APPLIES TO ALL COUNTRIES]

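### The by-indication variable puts prescribers for both RA and PsA into one indication by OneKey specialty, with no mapping given, although S3 already records both

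*Protocol*

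**What the plan says.** Section 8.3 (Variables, item 1) lists experience prescribing Xeljanz in the past 12 months and adds: "This variable will be used as a proxy for indication". It then sets a rule for the RA/PsA survey. An HCP with prescribing experience in both indications "will be classified in the indication that corresponds to the HCP’s highest specialty designation in the OneKey database".

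The RA/PsA questionnaire (Appendix 1) asks for the indication directly. S3 reads "Please indicate the diagnosis for which you prescribed tofacitinib in the past 12 months", offers one box for rheumatoid arthritis and one for psoriatic arthritis, instructs "Select all responses that apply", and is programmed as multiple punch.

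Section 8.7.1 names the variable among the possible stratification factors, subject to sample size: "experience prescribing Xeljanz (a proxy for indication), receipt and utilisation of the aRMM materials, and/or number of years in practice may be performed". The same section pools all primary analyses over countries, specialties and indications, and rules out statistical comparisons between indications.

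Section 8.3 recognises rheumatology, dermatology and other as specialties in the RA/PsA survey. Footnote 4, attached to the inclusion criteria in Section 8.2.2.1, admits prescribers outside the three named specialties.

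**The concern.** The rule replaces a direct answer with a database field. Every respondent who passes screening tells the survey whether tofacitinib was prescribed for RA, PsA or both. For those who answer both, the stratification variable drops that answer and takes a single indication from the OneKey specialty.

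The field cannot do this job. A rheumatologist who has just reported prescribing for both diseases shows that rheumatology does not correspond to one of them. A dual prescriber whose specialty is neither rheumatology nor dermatology has no indication to be sent to. No table or sentence in the protocol supplies the mapping.

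If the stratification is run, a column headed PsA would not describe the HCPs who prescribe for PsA. For dual prescribers it would be a specialty result under an indication label. Specialty is not itself in the list of stratification factors in Section 8.7.1, so a reader of the report would have little to warn them. The affected stratum would also be smaller, and its estimates less precise, than the collected data allow.

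**Working it through.** **1. The rule against the data collected**

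| S3 answer | Stratum under Section 8.3 | What S3 shows |
|---|---|---|
| RA only | RA | RA |
| PsA only | PsA | PsA |
| Both, rheumatology in OneKey | RA or PsA, not stated | RA and PsA |
| Both, dermatology in OneKey | PsA by implication (Section 8.5 links dermatologists with PsA) | RA and PsA |
| Both, other specialty | None defined | RA and PsA |

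If rheumatology goes to RA, dual-prescribing rheumatologists are missing from PsA. If it goes to PsA, they are missing from RA. One stratum is incomplete either way. PsA-only rheumatologists stay in PsA under both mappings.

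**2. The plan's own precision figure**

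Section 8.5 gives 5.7% for 300 completes at P = 50%. Half-width = 1.96 × √(0.25/n) = 0.98/√n. With n = 300 this is 0.98/17.32 = 5.66%, which reproduces the stated figure. The same formula is used below.

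**3. Illustration of the size**

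The documents give neither the rheumatologist share among completers nor the dual-prescribing share, so both are assumed:

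- 300 completes, all rheumatologists or dermatologists;
- rheumatologist share r from 30% to 90%;
- dual-prescribing share among rheumatologists d from 50% to 90%;
- every dermatologist prescribes for PsA, and no rheumatologist prescribes for PsA only;
- rheumatology is mapped to RA and dermatology to PsA.

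The 30% end has a documented anchor. Appendix 5 lists 9,132 rheumatologists and 21,099 dermatologists, and 9,132/(9,132 + 21,099) = 30%. Higher values of r are plausible because Section 8.5 expects fewer dermatologists to manage suitable patients.

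Formulas:

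- PsA stratum under the rule = 300(1 − r)
- PsA prescribers by S3 = 300(1 − r) + 300·r·d
- Share left out = 300·r·d / [300(1 − r) + 300·r·d]

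| r | PsA under the rule (half-width) | PsA by S3, d = 50% to 90% (half-width) | Left out |
|---|---|---|---|
| 30% | 210 (6.8%) | 255 to 291 (6.1% to 5.7%) | 45/255 = 18% to 81/291 = 28% |
| 50% | 150 (8.0%) | 225 to 285 (6.5% to 5.8%) | 75/225 = 33% to 135/285 = 47% |
| 70% | 90 (10.3%) | 195 to 279 (7.0% to 5.9%) | 105/195 = 54% to 189/279 = 68% |
| 90% | 30 (17.9%) | 165 to 273 (7.6% to 5.9%) | 135/165 = 82% to 243/273 = 89% |

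The range over the whole grid is about 18% to 89%.

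**4. Sensitivity to the PsA-only assumption**

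A second set of assumptions lets 5% of rheumatologists prescribe for PsA only and sets dermatologists at 5-30% of completers, with d again 50-90%. The PsA stratum is then about 29 to 100 under the rule against 172 to 290 by S3, and 51% to 90% are left out. At the low end the stratum falls under the size of 30 below which Section 8.9.5 doubts generalisability.

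**The case against.** The strongest reply is that little depends on this variable. All primary analyses are pooled over indications, the 80% criteria in Section 8.3 apply to the RA/PsA survey as a whole, no objective in Section 7 asks for a PsA-specific result, and the stratification is only something that may be done. All of this stands and limits the point to an optional table. A reader might infer that the headline effectiveness results are biased or that respondents are dropped from the study. The documents support neither.

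A reader might also infer that the protocol assigns rheumatologists to RA. It does not say so. That is the natural reading, since the only specialty-indication link in the text is between dermatologists and PsA. The firm defect is the missing mapping. The direction of the loss is conditional on the mapping chosen.

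Nor is S3 thrown away. Section 8.7.5 reports the seven prescribing-experience questions descriptively, and that count fits S2, S3 and Q1 to Q5, so the RA/PsA mix can still be shown. The knowledge and adherence items Q6 to Q11 concern tofacitinib in general, so a dual prescriber gives one set of answers and no PsA-specific knowledge is lost. What changes is who is counted in each stratum.

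Finally, a mutually exclusive, pre-specified classification is a legitimate aim. That is true, but S3 supplies one (RA only, PsA only, both) without borrowing from specialty. The rule is worded as something that will be done, so it governs whenever the stratification is run.

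**Conclusion.** The point holds for the by-indication stratification of the RA/PsA survey and for nothing beyond it. Section 8.3 fixes a rule that conflicts with the collected answers, depends on a mapping that the protocol does not give, and cannot place dual prescribers of other specialties. At least one indication stratum would omit dual prescribers whichever mapping is chosen.

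The 18-89% range rests entirely on assumed shares and on rheumatology being mapped to RA. A single large figure from high rheumatologist shares would overstate what is known: at the 30% share implied by the Appendix 5 counts, the loss is 18-28% and the half-width changes by about one percentage point or less. This is worth correcting before any by-indication table is produced, but it does not threaten the primary conclusions.

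**What to change.** In Section 8.3, replace the classification sentence with strata taken from S3: RA only, PsA only, and both. If any of these cells falls below 30, add summaries for any RA and any PsA prescribing. If a specialty view is wanted, report specialty (D1 or OneKey) as its own stratification factor and label it as such.

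The cost is one sentence in the protocol and one table shell. S3 and D1 are already collected, so neither the questionnaire nor the fieldwork changes, and dual prescribers of other specialties become classifiable. The downside is a risk of small cells in the three-way split, or overlapping groups in the any-RA and any-PsA summaries. The overlap is acceptable because Section 8.7.1 plans no comparison between indications.
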